### **7.3.2 Participant departure from study product administration schedule**

Every effort should be made to follow the study product administration schedule per the protocol. If a participant misses a study product administration and the visit window period for the study product administration has passed, that study product cannot be given. The participant should be asked to continue study visits. The participant should resume the study product administration schedule with the next study product administration unless there are circumstances that require further delay or permanent discontinuation of study product administration (see Sections 7.3.1 and 7.3.3).

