### **7.3.3 Discontinuing study product administration for a participant**

Under certain circumstances, an individual participant's study product administrations will be permanently discontinued. Specific events that will result in stopping a participant's study product administration schedule include:

- Co-enrollment in a study with an investigational research agent (rare exceptions allowing for the continuation of study product administration may be granted with the unanimous consent of the HVTN 128 PSRT)
- Clinically significant condition (ie, a condition that affects the immune system or for which continued study product administration and/or blood draws may pose additional risk), including but not limited to the following:
  - HIV infection
  - Any grade 4 local or systemic Solicited or Unsolicited AE that is subsequently considered to be related to study product;

- Any grade 3 clinical AE (exception: fever and subjective local and systemic symptoms) that is subsequently considered to be related to study product (upon review, the HVTN 128 PSRT may allow continuation of study product administration if the participant has grade 3 erythema and/or induration)
  - Any grade 3 or 4 lab abnormality confirmed by a repeated value that is subsequently considered to be related to study product
  - SAE that is subsequently considered to be related to study product administration
  - Clinically significant hypersensitivity or mAb reaction including but not limited to type 1 hypersensitivity reaction, urticaria, or serum sickness associated with study product. Consultation with the HVTN 128 PSRT is required prior to subsequent infusion following any hypersensitivity reaction associated with study product
- Investigator determination in consultation with Protocol Team leadership (eg, for repeated nonadherence to study staff instructions)

Participants discontinuing study product administration for reasons other than pregnancy and HIV infection should be counseled on the importance of continuing with the study and strongly encouraged to participate in follow-up visits and protocol-related procedures per the protocol for the remainder of the trial, unless medically contraindicated (see HVTN 128 SSP).

Participants who become pregnant during the study should be encouraged to participate in follow-up visits (see Section 9.13). Participants diagnosed with HIV infection during the study should be encouraged to participate in follow-up visits (see Section 9.14).

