7 STATISTICAL ANALYSIS

This section describes the final study analyses, unblinded as to treatment arm assignment. All analyses pertaining to safety and drug levels objectives of the study will be conducted with an intent-to-treat analysis that includes all randomized individuals per their randomization allocation. Additional analyses will be performed that account for the actual infusions and dose levels that each participant received. Analyses for primary endpoints will be performed using SAS and R. Additional software may be used to perform non-compartmental PK and population PK analyses (eg, Monolix). All other descriptive and inferential statistical analyses will be performed using SAS, or R statistical software.

No formal multiple comparison adjustments will be employed for multiple primary or secondary endpoints. Unless otherwise noted, all statistical tests will be 2-sided and will be considered statistically significant if $p < 0.05$.

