Comparisons of dose-amount-adjusted, IgG-normalized VRC07-523LS concentrations between visits (v2 vs. v5, v2 vs. v7, v2 vs. v9, v4 vs. v6, v4 vs. v8, v6 vs. v8) are made using the Wilcoxon Signed-Rank test, and comparisons between sexes at birth at visits 4 and 5 are made using the Wilcoxon Rank Sum test. Additionally, comparisons of body-weight-adjusted, IgG-normalized VRC07-523LS concentrations between treatment arms at visits 4 and 5 are made using the Wilcoxon Rank Sum test. Comparisons are made for the % penetration of protein-normalized VRC07-523LS between visits, and specimen types using Wilcoxon Signed-Rank test; and between treatment arms using Wilcoxon Rank Sum test; and between sex at birth, controlling for treatment arms using Van Elteren Test. Comparisons are conducted between levels normalized using actual total protein concentrations and those normalized using the U.S. reference protein concentration (70 g/L) with treatment arms (T1 and T2) pooled using the Wilcoxon Signed Rank Test. Linear mixed-effect regression analyses are performed modeling natural log-transformed concentrations as a function of time since most recent infusion, sex at birth, and treatment group. Linear regressions are performed modeling the difference between natural log-transformed concentrations between visits adjusting for the difference between number of days since last infusion at compared visits, as well as sex at birth and treatment group. P-values are adjusted for multiple comparisons by controlling the false discovery rate (FDR) using the Benjamini-Hochberg procedure [9]

and the q-value [10]. Results are significant if the adjusted p-value or q-value ≤ 0.05 . Comparisons are conducted for groups with at least 3 data points for paired test and at least 5 for unpaired test.

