8.3.1 List of Tables

- Comparisons of body weight at baseline (T1: VRC07-523LS 10 mg/kg vs T2: VRC07-523LS 30 mg/kg) using Wilcoxon Rank Sum Test, by sex at birth.
- Comparisons of body weight at baseline (Female vs Male) using Wilcoxon Rank Sum Test, by arm.
- Summary statistics (i.e., N, min, 25%ile, mean, median, 75%ile, max, geometric mean, standard deviation) of body-weight-adjusted IgG-normalized VRC07-523LS concentration for each specimen type, by specimen type, treatment arm, assigned sex at birth and visit.
- Summary statistics (i.e., N, min, 25%ile, mean, median, 75%ile, max, geometric mean, standard deviation) of body-weight-adjusted protein-normalized VRC07-523LS concentration for each specimen type, by specimen type, treatment arm, assigned sex at birth and visit.
- For secretions, dose normalized IgG-normalized VRC07-523LS concentrations comparisons between visits 4, 6, and 8 (Cmax after a different number of infusions) using Wilcoxon signed-rank test, by specimen type. P-values will be adjusted for multiple comparisons by controlling the false discovery rate (FDR) using the Benjamini-Hochberg (BH) procedure and the q-value. The unadjusted p-values, BH-adjusted p-values, and q-values will be reported.
- For secretions, dose normalized IgG-normalized VRC07-523LS concentrations comparisons between visits 2, 5, 7, and 9 (trough after a different number of infusions) using Wilcoxon signed-rank test, by specimen type. P-values will be adjusted for multiple comparisons by controlling the false discovery rate (FDR) using the Benjamini-Hochberg (BH) procedure and the q-value. The unadjusted p-values, BH-adjusted p-values, and q-values will be reported.
- For mucosal tissues, comparisons between visits 4 vs 8 dose normalized IgG-normalized VRC07-523LS concentrations (Cmax after a different number of infusions) using Wilcoxon

signed-rank test, by specimen type. P-values will be adjusted for multiple comparisons by controlling the false discovery rate (FDR) using the Benjamini-Hochberg (BH) procedure and the q-value. The unadjusted p-values, BH-adjusted p-values, and q-values will be reported.

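### SAP 8.3.1 reads the number of infusions off the visit number, so missed or stopped infusions can dilute or mask mucosal accumulation in the paired tests

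*SAP*

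**What the plan says.** **Labels by visit.** SAP 8.3.1 lists, for secretions, "comparisons between visits 4, 6, and 8 (Cmax after a different number of infusions) using Wilcoxon signed-rank test" and "comparisons between visits 2, 5, 7, and 9 (trough after a different number of infusions) using Wilcoxon signed-rank test". The tissue tables (visits 4 vs 8 and 2 vs 9) and the percent-penetration tables use the same labels. The methods text in SAP 8.3 names the pairs as "v2 vs. v5, v2 vs. v7, v2 vs. v9, v4 vs. v6, v4 vs. v8, v6 vs. v8".

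**Population.** SAP 7 prescribes for drug levels an "intent-to-treat analysis that includes all randomized individuals per their randomization allocation". Protocol 6.4.4.1 likewise takes randomized participants whatever number of administrations they had. SAP 8.3 names no population of its own. Its exclusions cover pre-treatment, hemoglobin-contaminated and unreliable samples, not missed or stopped infusions. SAP 8.1 restricts the primary serum analysis to participants who had received the scheduled infusions by the time of the sample.

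**What happens after a missed or stopped infusion.** Under Protocol 7.3.2, once the window has passed, "that study product cannot be given. The participant should be asked to continue study visits", and "The participant should resume the study product administration schedule with the next study product administration". Under Protocol 7.3.3, participants whose product is stopped for reasons other than pregnancy or HIV infection are "strongly encouraged to participate in follow-up visits and protocol-related procedures per the protocol for the remainder of the trial", unless medically contraindicated. Mucosal sampling stops in pregnancy and HIV infection (Protocol 9.13, 9.14), and participants may decline it (Protocol 9.6).

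**The concern.** A comparison of peaks after one, two and three infusions has that meaning only if the participant received one, two and three infusions. The plan takes the count from the visit number, while the protocol expects some participants to be sampled without the scheduled infusion. Such a participant contributes a large fall that reflects the absent dose, not the kinetics after repeated dosing. In a signed-rank test on about 12 pairs, that fall is likely to take the largest rank.

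At stake is how the trial describes mucosal accumulation and persistence over repeated infusions. Because SAP 8.3 names no population while SAP 7 and 8.1 differ, the population could also be chosen after the data are seen.

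**Working it through.** **1. The plan's own figure.** The documents give no sizing for accumulation. The only mucosal sizing is the correlation power in Protocol Table 6-3. For r = 0.5 and n = 24: Z' = arctanh(0.5) + 0.5/46 = 0.560; critical r = 0.404, arctanh = 0.429; (0.560 − 0.429) × √21 = 0.60, so power is 72.6%, as stated. It says nothing about the paired visit tests.

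**2. Which samples can be mislabelled** (days from Protocol Table 9-1).
- Visits 4 and 5: none. SAP 4 limits the randomized cohort to participants who received product, and visit 5 is sampled before infusion 2.
- Infusion 2 missed: visit 6 (day 126) is 18 weeks after infusion 1, not 2 weeks after infusion 2. Visit 7 is 32 weeks after infusion 1. Visit 8 is still 2 weeks after an infusion, but after the second and not the third.
- Infusion 3 missed: visit 8 is 18 weeks and visit 9 is 32 weeks after infusion 2.
- Stopped after infusion 1: visit 8 (day 238) is 34 weeks after the only dose.

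**3. Size of one participant's fall.** The text supplied gives no human half-life, so t is assumed. With mono-exponential decay and the 112-day interval, d = 2^(−112/t). Full dosing gives visit 6 / visit 4 = 1 + d; a missed infusion 2 gives d.

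| Assumed t (days) | Full dosing | Infusion 2 missed |
|---|---|---|
| 30 | 1.075 | 0.075 |
| 40 | 1.144 | 0.144 |
| 48 | 1.20 | 0.20 |
| 60 | 1.27 | 0.27 |
| 112 | 1.50 | 0.50 |

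**4. Exact signed-rank test, noise-free.** p = 2 × (number of subsets of ranks 1 to n with sum ≤ W−) / 2^n. Here n = 12 (semen, cervical and vaginal specimens come from one sex, about half of 24), and fallers take the largest ranks.
- None: W− = 0, p = 2/4096 = 0.0005.
- One: W− = 12, 70 subsets, p = 140/4096 = 0.034.
- Two: W− = 12 + 11 = 23, 478 subsets, p = 956/4096 = 0.23.

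The rank sum changes direction only at 4 of 12 (42 of a total 78). It is significantly reversed only at 8 of 12. For n = 24 (rectal specimens, both sexes): p = 0.0022 with two, 0.019 with three, 0.089 with four; a significant reversal needs 12.

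**5. With noise, and half-life and accumulation tied together.** Visit 6 vs visit 4, n = 12, SD of the log ratio 0.4 (assumed), two-sided 5% before FDR. The geometric mean ratio with one miss is exp{[11 ln(1 + d) + ln d]/12}.
- t = 48 d: [11 × 0.181 − 1.618]/12 = 0.031, so the ratio falls from 1.20 to 1.03. Simulated power falls from about 27% to 2%; with the pair left out (n = 11) it is about 24%.
- t = 112 d: [11 × 0.405 − 0.693]/12 = 0.314, so the ratio falls from 1.50 to 1.37. Power falls from about 86% to just under 50%.
- t = 40 d: the ratio falls from 1.144 to 0.962. The point estimate drops below 1.

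At n = 24 and t = 48 d, one miss moves power from about 55% to 30% and the ratio from 1.20 to 1.11.

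**6. Frequency.** The documents give no missed-infusion rate. The 17% and 10–15% in Protocol 6.1 are missing-assay-data rates. For scale only, at an assumed 5% to 17% per participant, the chance of at least one miss among 12 is 1 − 0.95^12 = 46% to 1 − 0.83^12 = 89%.

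**The case against.** **The plan already accounts for infusions elsewhere.** SAP 7 promises additional analyses based on the infusions actually received, and Protocol 6.4.4.1 allows analyses limited to full recipients. In SAP 8.3 the mixed model uses time since the most recent infusion, and the visit-difference regression adjusts for days since last infusion. This mitigates the largest distortion, elapsed time. It does not repair the listed signed-rank tables, none of which has an actual-infusion counterpart, and neither model includes the number of infusions.

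**Accumulation is not a stated objective.** Primary objective 2 concerns detectable levels being reached and maintained, and serum–mucosa correlation; secondary objective 1 compares dose regimens. Accumulation appears in the rationale (Protocol 4.2.1, 4.3). That stands and limits the importance. The tests are nevertheless planned, with significance claims attached.

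**Stronger readings the documents do not support.**
- A reader might infer that a miss reverses the accumulation result. A significant reversal needs about half or more of the participants to miss. The trough pairs named in the methods text are all against pre-dose visit 2, so a miss shrinks them and cannot turn them round.
- A reader might infer that everyone's samples carry a wrong count. Only visits 6 to 9 can, and only for participants without the scheduled infusions. Their inclusion follows from the SAP 7 default, because SAP 8.3 itself is silent.
- A reader might pair 1.5-fold accumulation with a 30-day half-life and find a far larger loss. Under the same decay model 30 days gives 1.075, and 1.5 requires 112 days.
- Protocol 7.3.3 encourages continued procedures; it does not guarantee the samples.

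**Conclusion.** The point holds as a should-fix. Followed as written, the plan places samples at visits 6 to 9 in the paired peak and trough tests with an infusion count that may be wrong. The expected harm is dilution or masking of accumulation, sometimes with a ratio below 1. It is greatest for one-sex specimens with about 12 pairs, where one or two misses are enough; rectal specimens with about 24 pairs are less affected.

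The exact p-values in step 4 assume that all other pairs rise and that the fallers take the largest ranks. The ratios and power rest on assumed half-life, log SD and mono-exponential decay, and how often infusions are missed is unknown. Where accumulation is small, power is low even with full dosing, so the shift in the estimate matters more than the lost significance. The effect on percent penetration was not quantified; a missed infusion lowers serum as well as mucosa, so the ratio may be less distorted even though its label is wrong.

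**What to change.** In SAP 8.3:
- State the analysis population and reconcile it with SAP 7 and 8.1.
- For the paired peak and trough tests in 8.3.1, including tissue and percent penetration, include a participant's pair only if all infusions due by the sampled visits were received and each post-infusion sample falls in the scheduled window after the last one. SAP 8.1 already sets such a condition for serum.
- Keep the as-randomized summaries by visit, and footnote the number of participants without the scheduled infusions.
- Add the number of infusions received to the mixed model and the visit-difference regression.

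The cost is SAP wording and one variable derived from the infusion records. Some tests lose a pair or two, and their results become conditional on infusions received, which the tables should state.

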For continuous assay data (eg, levels of VRC07-523LS in serum and mucosa), graphical and tabular summaries of the distributions by treatment arm and timepoint will be made. Scatterplots and measures of association (eg, Spearman's rank and Pearson's linear correlation coefficients) and their 95% CIs will be constructed within each timepoint for every pair of serum and mucosa drug levels. Regression models may be used to describe association between two variables (eg, VRC07-523LS levels measured in a mucosal site versus VRC07-523LS levels in the serum), potentially adjusting for important confounders if needed. Independent samples (eg, VRC07-523LS levels measured in different treatment groups) may be compared using nonparametric tests (eg, Wilcoxon rank-sum or Mann-Whitney tests), whereas paired samples (eg, VRC07-523LS levels measured in mucosal secretions before and after the first drug administration) will be compared using Wilcoxon's signed rank test. If the normality assumption appears satisfied, two-sample *t*-tests with unequal variances, or parametric analysis of variance (ANOVA), or analysis of covariance (ANCOVA) adjusting for important covariates, may be used instead of the nonparametric tests when comparing independent groups. Likewise, the comparison of paired samples may be accomplished using one-sample *t*-tests. An appropriate data transformation (eg, logarithmic) may be applied prior to hypothesis testing to better satisfy analysis assumptions. For the analysis of correlation between two continuous assay variables over time, cross-correlation of the two variables with different time lags may also be calculated and visually displayed. Similar analyses stratifying by sex assigned at birth will be performed. Inference from these analyses will have limited power due to the small sample sizes of the groups.

The analysis of categorical variables derived from assay measurements (eg, whether VRC07-523LS levels are above a limit of detection or prebaseline levels) will be performed by tabulating the frequency of each category for each assay by group at each timepoint at which an assessment is performed. Frequencies will be presented with their corresponding 95% CI estimates calculated using the score test method (57).

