3.2 Secondary objectives and endpoints

Secondary objective 1:

- To compare dose regimens of VRC07-523LS delivery for their ability to sustain mucosal mAb levels at serial timepoints post repeat administration

Secondary endpoint 1:

- Levels of VRC07-523LS in genital and rectal secretions and tissue at specified timepoints

Secondary objective 2:

- To determine whether ADA can be detected in serum

Secondary endpoint 2:

- Serum concentration of ADA in each group measured at multiple timepoints from baseline through the final study visit

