8.1.1 List of Tables

- Table 1, Counts of concentrations > LLOQ

- Table2, Descriptive statistics (i.e., sample size (N), geometric mean, median, min, max and IQR) of participant-level mAbs concentrations by treatment groups, visits, among the per protocol cohort, including values below the LLoQ.
- Comparison of dose-normalized concentrations between groups within time points

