- For mucosal tissues, comparisons between visits 2 vs 9 dose normalized IgG-normalized VRC07-523LS concentrations (trough after a different number of infusions) using Wilcoxon signed-rank test, by specimen type. P-values will be adjusted for multiple comparisons by controlling the false discovery rate (FDR) using the Benjamini-Hochberg (BH) procedure and the q-value. The unadjusted p-values, BH-adjusted p-values, and q-values will be reported.
- For secretions, body-weight-adjusted IgG-normalized VRC07-523LS concentrations comparisons between treatment groups at visits 4 and 5 using Wilcoxon signed-rank test, by specimen type with sex at birth combined. P-values will be adjusted for multiple comparisons by controlling the false discovery rate (FDR) using the Benjamini-Hochberg (BH) procedure and the q-value. The unadjusted p-values, BH-adjusted p-values, and q-values will be reported.
- For mucosal tissues, body-weight-adjusted IgG-normalized VRC07-523LS concentrations comparisons between treatment groups at visit 4 using Wilcoxon signed-rank test, by specimen type with sex at birth combined. P-values will be adjusted for multiple comparisons by controlling the false discovery rate (FDR) using the Benjamini-Hochberg (BH) procedure and the q-value. The unadjusted p-values, BH-adjusted p-values, and q-values will be reported.
- Comparisons for body-weight-adjusted IgG-normalized VRC07-523LS concentration at peak timepoints (T1 vs T2) using Wilcoxon rank sum test, by specimen type and for (1) both assigned sexes at birth combined for rectal biopsies and rectal secretions and (2) each assigned sex at birth separately for other specimen types. P-values will be adjusted for multiple comparisons by controlling the false discovery rate (FDR) using the Benjamini-Hochberg (BH) procedure and the q-value. The unadjusted p-values, BH-adjusted p-values, and q-values will be reported.
- For rectal secretions, dose-amount-adjusted IgG-normalized VRC07-523LS concentrations comparisons at visit 4 and 5 among different sexes, using Wilcoxon rank sum test, by specimen type. P-values will be adjusted for multiple comparisons by controlling the false discovery rate (FDR) using the Benjamini-Hochberg (BH) procedure and the q-value. The unadjusted p-values, BH-adjusted p-values, and q-values will be reported.

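### SAP 8.3.1 names a paired test for two comparisons of independent dose arms and lists no dose comparison of mucosal levels at the repeat-dose troughs

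*SAP*

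**What the plan says.** The table list in SAP 8.3.1 has two entries that compare arms with a paired test. Both concern body-weight-adjusted, IgG-normalized levels. For secretions it lists "comparisons between treatment groups at visits 4 and 5 using Wilcoxon signed-rank test, by specimen type with sex at birth combined". For mucosal tissues it lists "comparisons between treatment groups at visit 4 using Wilcoxon signed-rank test, by specimen type with sex at birth combined". A third entry compares the same measure "concentration at peak timepoints (T1 vs T2) using Wilcoxon rank sum test".

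The Statistical methods text of SAP 8.3 covers the same measure and says that "concentrations between treatment arms at visits 4 and 5 are made using the Wilcoxon Rank Sum test". Protocol 6.4.4.1 agrees: "Independent samples (eg, VRC07-523LS levels measured in different treatment groups) may be compared using nonparametric tests (eg, Wilcoxon rank-sum or Mann-Whitney tests". SAP 8.3 also sets minimum counts that depend on the type of test: "Comparisons are conducted for groups with at least 3 data points for paired test and at least 5 for unpaired test".

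Secondary objective 1 (SAP 3.2) is to compare the dose regimens "for their ability to sustain mucosal mAb levels at serial timepoints post repeat administration". For serum, SAP 8.1.1 lists "Comparison of dose-normalized concentrations between groups within time points". SAP 8.3.1 has no equivalent entry for mucosal samples.

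**The concern.** **The test.** A signed-rank test needs pairs. Each participant is randomized to one arm, and neither document defines a match between a T1 and a T2 participant. A programmer working from the table list would have to invent a pairing, and the p-value would change with it. The paired label also lowers the count needed to run a test from 5 to 3. Visit 4 should also be reached by the rank-sum entry for peak timepoints, so the conflict matters most for visit 5 secretions, the only trough with any listed arm test of levels.

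**The coverage.** Visit 5 is the trough after one infusion. The troughs after repeat dosing are visits 7 and 9. These visits show whether a dose sustains mucosal levels, and no T1 versus T2 test of levels is listed there.

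**A minor point.** SAP 8.3 contrasts the troughs only with visit 2, while SAP 8.3.1 can be read as also comparing visits 5, 7 and 9 with each other.

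**Working it through.** The documents state no sample size or power for an arm comparison of mucosal levels, so there is no planned figure to reproduce.

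**Inputs.** There are 12 participants per arm (Protocol 6.1). A single-sex specimen has about 12 × 0.5 = 6 per arm. Under the 40% to 60% sex imbalance in Protocol 6.1.2 this is 12 × 0.4 = 4.8 to 12 × 0.6 = 7.2, or about 5 to 7. Missing data run at 10-15% or 17% (Protocol 6.1). Those rates are not stated to be mucosal, and I assume missingness is independent between participants.

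**Smallest attainable two-sided p, unadjusted.** Signed-rank is 2/2^n; rank-sum is 2/C(2n,n).

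| n per arm | Signed-rank | Rank-sum |
|---|---|---|
| 5 | 2/32 = 0.0625 | 2/252 = 0.008 |
| 6 | 2/64 = 0.031 | 2/924 = 0.002 |
| 7 | 2/128 = 0.016 | 2/3432 = 0.0006 |

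At 4 and 3 pairs the signed-rank minimum is 0.125 and 0.25.

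**Chance that at least one arm has 5 or fewer.** At 6 per arm, both arms must be complete to avoid it: 1 − 0.90^12 = 0.718 at 10% missing and 1 − 0.83^12 = 0.893 at 17%. At 7 per arm, each arm may lose one: 1 − (0.90^7 + 7 × 0.10 × 0.90^6)^2 = 0.277 at 10%, and 0.564 at 17%. At 5 per arm it is certain. At 12 per arm (rectal samples) it is below 0.3%.

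**Chance that the smaller arm has 3 or 4**, where the paired label runs a test that the unpaired rule would not: 5-19% at 7 per arm, 21-45% at 6 and 63-77% at 5.

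**Power.** This was simulated (40,000 normal-log datasets, exact critical values, arbitrary pairing, unadjusted two-sided 0.05). The 3-fold difference and the log SDs of 0.5, 0.8 and 1.1 are my assumptions.

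| n per arm | Rank-sum, % | Signed-rank, % |
|---|---|---|
| 5 | 76 / 37 / 21 | 0 / 0 / 0 |
| 6 | 89 / 51 / 30 | 69 / 34 / 19 |
| 7 | 94 / 57 / 34 | 90 / 54 / 33 |
| 12 | 99.9 / 87 / 61 | 99.7 / 83 / 56 |

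Simulated type I error, rank-sum versus signed-rank, is about 4.0% vs 3.0% at n = 6, 3.7% vs 4.6% at n = 7 and 4.5% vs 4.2% at n = 12.

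**Dependence on the pairing.** In the same scenarios, two random pairings of one dataset disagree at 0.05 with probability 23/23/16% at n = 6, 9/21/18% at n = 7 and 0.5/11/16% at n = 12.

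**Coverage.** Post-dose cells: 3 secretions × 6 visits (4 to 9) + 3 tissues × 3 visits (4, 8, 9) = 27. If peak means the visits that the SAP labels Cmax (4, 6, 8 for secretions; 4, 8 for tissues), arm tests of levels are listed for 9 + 6 = 15 cells, plus 3 for visit 5 secretions, giving 18. If peak means visit 4 only, the count is 3 + 3 + 3 = 9. On either reading, the 3 × 2 + 3 = 9 repeat-dose trough cells have none.

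**Why the mixed model does not fill the gap.** Its stated terms are time since most recent infusion, sex and treatment group. Visits 5, 7 and 9 fall at nominal days 112, 224 and 336, after infusions on days 0, 112 and 224, so each is 112 days after the last infusion. The model as described treats them alike and states no arm contrast at any of them.

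**The case against.** The signed-rank wording is very probably a slip. The methods text, the protocol, the neighbouring peak entry and the parallel penetration entries all say rank-sum, and without a pairing variable the entry cannot be run as written. Type I error is not inflated, and visit 4 should be covered elsewhere. The material loss is then confined to semen and cervicovaginal secretions at visit 5. Protocol 6.1 also aims for at least about 50% female participants, so about 5 per arm by design would apply mainly to semen. All of this limits the size of the problem. It does not make the listed rule right, and missing data can still reduce 6 per arm to 5.

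On coverage, other analyses bear on the objective: a regression of between-visit change with a treatment term, detection frequencies by group with confidence intervals, exploratory population PK models, and peak tests that may reach visits 6 and 8. None is a comparison of trough levels between arms. The change regression does not specify its visit pairs, and the detection frequencies are summaries by arm. SAP 8.1 does plan geometric means with 95% CIs, and its wording includes mucosal concentrations. The mucosal tables in SAP 8.3.1, however, list the geometric mean and SD without an interval.

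Two cautions stand. The serum entry is dose-normalized, whereas a body-weight-adjusted comparison asks a different question. And the SAP's truncation rules already report that no post-baseline serum value is below the LLOQ, so some results were known when it was written, and added tests may need to be labelled post hoc.

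**Conclusion.** Both parts hold, and the plan should be corrected. The two entries contradict the SAP's own methods text and the protocol. Under the paired test, the loss at unadjusted 0.05 is total at 5 per arm, moderate at 6 and small at 7 or 12. The minimum p-values are exact. The power figures rest on the assumed 3-fold difference and log SDs, and the missing-data probabilities on the protocol's general rates and independence. For the repeat-dose troughs, estimates by arm are planned but no dose comparison of levels is listed in any of the nine cells, although that is what secondary objective 1 concerns. This does not invalidate the trial.

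**What to change.** 1. In SAP 8.3.1, replace signed-rank with rank-sum in the two T1 versus T2 entries (secretions at visits 4 and 5; tissues at visit 4).
2. Add T1 versus T2 rank-sum comparisons of body-weight-adjusted, IgG-normalized levels at visits 7 and 9 for secretions and visit 9 for tissues. If a model is preferred, give it a treatment-by-visit or treatment-by-infusion-number term and state the contrasts.
3. State in both SAP 8.3 and SAP 8.3.1 which pairs of trough visits are compared (minor).

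The cost is SAP wording and nine table rows from samples already scheduled. Nine more p-values (6 secretion, 3 tissue) enter the FDR adjustment. Six of the nine rows are single-sex, and the minimum of five per group may stop them: at 10-17% missing, at least one arm falls below 5 in 22-47% of cases at 6 per arm, 5-19% at 7 and 65-84% at 5. The planned geometric means with 95% CIs would then carry the comparison, so those intervals should appear in the mucosal tables. If mucosal results have already been seen, label the added tests accordingly.
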